1.2 Name and Description of Intervention

The intervention will incorporate behavioral economic approaches utilizing AH to improve frequency of early parent-child shared reading through text messages. The intervention consists of daily text messages for 8 weeks in 3 AH intervention groups. The text messages were part of the aforementioned trial on early literacy promotion (see Appendix 1).

Group 1 of the program will consist of daily text messages on shared reading, which will be sent to participants using the Way to Health Platform. Participants will be asked to reply to the text message on daily shared reading activities including the titles of the books and time spent reading (see Appendix 1).

Group 2 will consist of Group 1 plus personalized coaching. Personalized coaching content will be made available to participants through links in the text messages.

Group 3 will consist of Group 2 personalized coaching plus availability of a weekly lottery. The lottery is related to principles of behavioral economics so that participants in group 3 will be externally motivated. The lottery is testing a methodology and is not a non-permissible form of payment. Participants who report back that they read on a particular day will be entered into a weekly drawing to receive \$20. Each reported daily reading behavior will provide a single lottery entry so that participants who report they read all 7 days in a given week will have 7 entries in the weekly drawing. Lottery entries will begin on Mondays and close at 12:00 AM on Sundays for all 8 weeks of the program. The following Monday morning the lottery will be drawn. The participants in Group 3 will begin their 8- week intervention the first Monday after enrollment.

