After conducting the rapid-cycle design for phase 1, forty-five eligible children and their parents will be consented and enrolled in the study. In the event that the baseline visit cannot be completed in-person an alternative method of obtaining informed consent electronically through REDCap will be used. Following informed consent and completion of baseline surveys, participants will be stratified by site and randomized 1:1:1 to receive one of the 3 AH interventions for an 8-week duration. Using a similar recruitment strategy, we were able to successfully recruit 120 (81%) of 148 low-income infants and their parents who were approached for the aforementioned study on early literacy promotion.

Group 1 will consist of daily text messages on shared reading, which will be sent to participants using the Way to Health Platform. Participants will be asked to reply to the text message on daily shared reading activities including the titles of books and time spent reading. Group 2 will consist of Group 1 plus personalized coaching. Personalized coaching content will be made available to participants through links in the text messages and will provide comparisons of their reading frequency with that of other participants. These comparisons will be blinded to preserve confidentiality. Finally, Group 3 will consist of Group 2 plus availability of a weekly lottery. Group 3 participants who report back that they read on a particular day will be entered into a weekly drawing to receive \$20. Each reported daily reading behavior will provide a single lottery entry so that participants who report they read all 7 days in a given week will have 7 entries in the weekly drawing.

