3.1.3 Randomized Trial

All participants across groups will be asked to report on daily reading behaviors by replying to daily text messages. In addition, participants will be asked to complete study measures using a RedCap survey at baseline and following the 8-week intervention period. Responses to daily reading text messages will be provided by the Way to Health platform and will be assessed as the mean overall number of days/weeks of reading for each group. Participants will also be provided with an opt out of the daily text messages option if they no longer desire to receive daily text messages. Participants will be queried at follow-up on their overall satisfaction (5-point Likert scale) with their intervention group and asked to answer survey questions regarding likes and dislikes concerning the intervention group they received following the intervention period. The survey questions at the end of phase 2 will be based on input from the rapid-cycle design process of phase 1 interviews.

At baseline, parents will complete a measure of demographics (child and parent age, race/ethnicity, sex, highest education completed, and family income category) (see Appendix 2). To explore differences in the home reading environment, parents will complete the Read subscale of the StimQ, a validated 14-item parent report measure of the home reading environment, at baseline and follow-up.²³ To explore differences in parenting stress, participants will complete the Parenting Stress Index-short form (PSI-SF), a validated 36-item parent report of parenting stress, at baseline and following the 8-week intervention in order to assess changes.²⁴ Finally to explore differences in child language and socio-emotional development, parents will complete at follow-up the MacArthur Communicative Development Inventory (CDI), a validated parent-report scale of early language development, and the Devereux Early

Childhood Assessment (DECA), a validated 33-item parent report of socio-emotional problems.^{25,26}

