6.4.3 Analysis of Primary Outcomes of Interest

6.4.3.1 Specific Aim 1

Primary outcomes:

To determine the feasibility of each group of the intervention, we will assess the proportion of participants who receive and report a daily reading behavior each week across all groups, the proportion of participants who access coaching content in group 2 & 3, and the proportion of participants who participate in the weekly lottery in group 3. To determine acceptability of the intervention, we will assess the number of participants who opt out of the daily text messages and query participants on their overall satisfaction (5-point Likert scale) with their intervention group and provide survey questions regarding likes and dislikes concerning the intervention group they received following the intervention period. The survey questions at the end of phase 2 will be based on input from the rapid-cycle design process of phase 1 interviews. Differences in weekly reading frequency and satisfaction scores between groups will be assessed using standard inferential statistics and intention-to-treat analysis. Survey question responses will be assessed using qualitative methods in which codes will be developed and emerging themes identified by consensus of investigators using NVivo software.

Secondary outcomes:

To explore differences in reading frequency, the home reading environment, parenting stress, and child language and socio-emotional development, we will examine differences in mean weekly reading frequency, mean changes in StimQ Read Subscale scores and PSI-SF scores, and mean CDI and DECA scores between groups using standard inferential statistics and intention-to-treat analysis. In addition, effect sizes will be computed to assess differences between Group 1 and each of the other 2 groups and to power future studies.

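### Reading frequency is taken only from voluntary text replies, with no rule for days without a reply, so a difference between arms in replying can appear as a difference in reading.

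*Combined protocol and SAP*

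**What the plan says.** Section 3.1.3 makes text replies the data source in every arm: "All participants across groups will be asked to report on daily reading behaviors by replying to daily text messages". The replies are supplied by the messaging platform and the outcome "will be assessed as the mean overall number of days/weeks of reading for each group". Section 1.2 says parents will be asked to "reply to the text message on daily shared reading activities including the titles of the books and time spent reading"; the message text itself is in Appendix 1, which is not part of the supplied text.

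Section 6.4.3.1 uses this outcome twice. Under the primary outcomes: "Differences in weekly reading frequency and satisfaction scores between groups will be assessed using standard inferential statistics and intention-to-treat analysis". Under the secondary outcomes: "we will examine differences in mean weekly reading frequency". It then plans effect sizes for Groups 2 and 3 against Group 1, to be used in powering later studies.

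The arms differ in what might prompt a reply. Section 3.1.2 gives Group 2 coaching links and comparisons of their reading frequency with that of other participants. Group 3 receives the same plus a lottery, in which "Each reported daily reading behavior will provide a single lottery entry".

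On missing data, Section 6.3 deals with preventing dropout and loss to follow-up. No section says what happens to a day on which a parent who is still receiving texts sends nothing.

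**The concern.** A reported reading day requires two things: the parent read, and the parent replied. The planned summary does not separate them. Coaching and comparison with other families could plausibly change how often parents reply without changing how often they read, so Group 2 v Group 1 is exposed even though no lottery applies there. The same replies also serve as the feasibility measure in Section 6.4.3.1. The plan thus treats replying as something that may vary, and then uses the same data stream as the measure of reading.

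Intention-to-treat does not settle the matter. Scoring silence as zero gives every parent a value but mixes replying with reading. Using answered days leaves a parent who never replies with no value. Table 1 and Section 4.2 list no text reporting before the intervention, so there is no baseline value of this outcome to adjust for.

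What is at stake is the exploratory reading comparison and, more importantly, the effect sizes carried into the next trial's sample size.

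**Working it through.** The plan states no figure for reply rate, reading rate or SD, and Section 6.4.2 says no power calculation is needed. There is therefore nothing to reproduce. The check is what each simple scoring rule does when true reading is identical in two arms.

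**From the documents:** 15 parents per arm (Section 6.4.2); daily texts for 8 weeks (Section 1.2), so 8 × 7 = 56 possible replies per parent.

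**Assumed:** true reading of 4 days/week in both arms (range 3 to 5), and the reply rates shown.

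**Rule A: silent day scored as no reading, replying unrelated to reading.** Counted days = true days × reply rate.

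| Reply rates | Counted days/week | False gap | False gap if true reading is 3 to 5 |
|---|---|---|---|
| 70% v 80% | 4 × 0.7 = 2.8 v 4 × 0.8 = 3.2 | 0.4 | 0.3 to 0.5 |
| 60% v 80% | 4 × 0.6 = 2.4 v 4 × 0.8 = 3.2 | 0.8 | 0.6 to 1.0 |

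A simulation put this on the trial's scale: 4,000 runs, 15 per arm, 56 days, assumed beta variation between parents in both reading and replying, and a two-sided t-test at an assumed 0.05. It gave false-positive rates of about 5% with equal reply rates (60% in both arms), 11% for 70% v 80%, and 34% for 60% v 80%. The spurious standardised differences in the last two cases were about 0.28 and 0.60.

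**Rule B: mean over answered days.** This equals scoring each parent's silent days at that parent's own answered-day rate. If replying is unrelated to reading, both arms give 4.0 and the simulated false-positive rate stays at about 5%. If replying depends on reading, let *a* = P(reply | read), *b* = P(reply | did not read) and *p* = 4/7. The mean is 7*pa* / (*pa* + (1 − *p*)*b*).

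- First arm, *a* = *b* = 0.7: 7 × 2.8 / (2.8 + 2.1) = 4.0. Counted days 2.8; overall reply rate 4.9/7 = 70%.
- Second arm, *a* = 0.9, *b* = 0.7: 7 × 3.6 / (3.6 + 2.1) = 4.42. Counted days 3.6; overall reply rate 5.7/7 = 81%.
- Second arm, *a* = 0.9, *b* = 0.4: 7 × 3.6 / (3.6 + 1.2) = 5.25. Counted days 3.6; overall reply rate 4.8/7 = 69%.

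Either version of the second arm shows more reading than the first under both rules, with no true difference. In the last case the overall reply rates are almost equal (70% v 69%).

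**The case against.** The strongest reply is that the point fills a silence with the worst assumption. Three stronger readings are tempting, and the documents support none of them.

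- A reader might infer that the text asks only what was read, so a parent who did not read has nothing to send. Section 1.2 says the reply covers reading activities, with titles and time as included items. That list is not exhaustive, time can be answered with zero, and the wording is in an appendix we cannot see. An explicit 'no' may already exist.
- A reader might infer that the plan scores silence as no reading. That is what a plain count would do, but no section states it.
- A reader might infer that reading is understated in every arm. That needs both zero-scoring and accurate self-report. These are unverified parent reports, and over-reporting would push the other way.

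It is also fair to say that the comparison is exploratory (Section 2.2) in a pilot of 45, that every reply rate above is assumed, and that nothing in the documents shows coaching moves replies by 10 or 20 points. Section 6.4.3.1 already reports weekly reporting as a feasibility outcome, and StimQ-Read does not depend on texts.

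These arguments limit the claim but do not remove it. Even if the text accepts a 'no', silent days still have no rule. The feasibility proportion is not days answered per parent, and StimQ-Read measures the home reading environment, not days per week. The exploratory label does not protect effect sizes that are to power later studies.

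**Conclusion.** The point holds as a gap in the outcome definition. The plan gives no scoring rule or denominator for unanswered days, and either simple rule can turn a difference in replying into an apparent difference in reading. Under a plain count with equal true reading of 4 days/week, the false gap is 0.4 days/week at 70% v 80% and 0.8 at 60% v 80%. These sizes rest wholly on assumed reply rates, and the first set also assumes that replying is unrelated to reading. No stated figure in the plan is wrong.

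A reader might infer that a reading difference is safe to claim when both scorings point the same way. It is not. With no true difference, the example above gives 2.8 v 3.6 by count and 4.0 v 4.4 by answered days. Where replying is unrelated to reading, the answered-day means are equal, so the sign of their observed difference is chance and would match the false count about half the time. The two scorings are a sensitivity range, not bounds on the truth.

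**What to change.** 1. Confirm that the daily text in all three arms (Appendix 1) accepts an explicit 'did not read' or 0-minute reply, and add it if it does not. This has to be in place while the texts are being sent, because it cannot be recovered afterwards.
2. In Section 6.4.3.1, report by arm the days answered per week and the number of parents who never reply, beside reading frequency.
3. Give the between-group difference and the effect size under both scorings: silent days as no reading, and silent days at the parent's own answered-day rate, with parents who never reply reported separately. Present the pair as a sensitivity range. Do not attribute a difference to reading when it depends on the scoring or when reply rates differ between arms. Similar reply rates do not by themselves establish a reading effect, as the 70% v 69% case shows.

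The cost is at most one line in the message template, a short addition to the analysis section, and a second pass of the same analysis on data the platform already holds. The downside is a less clear-cut exploratory reading result.

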3.2 Allocation to Treatment Groups

Participants will be recruited at the time of a well child visit for their infant using a recruitment flyer and will undergo written informed consent at their first visit. Caregivers of eligible children will be consented in person or electronically through REDCap. Following informed consent and completion of the baseline surveys participants will be randomized 1:1:1 to one of 3 AH groups: 1) daily text message reminders on shared readings using the Way to Health Platform or 2) daily text message reminders plus personalized coaching and social comparisons through links in the text messages or 3) daily text message reminders, coaching and the availability of a weekly lottery. Randomization will be accomplished in advance using computer generated numbers. Allocation concealment (blinding of the treatment assignment) will be implemented and sealed, opaque envelopes, along with stratification, and randomly permuted blocks of unequal sizes (to prevent providers and patients from manipulating the randomization).

3.3 Study Duration, Enrollment and Number of Sites

3.3.1 Duration of Study Participation

The study duration for Phase 1 of the study will be approximately 30 minutes. For Phase 2, the intervention duration will be 8 weeks for the intervention, but total study duration will last 12 weeks to allow for completion of follow-up measures.

3.3.2 Total Number of Study Sites/Total Number of Subjects Projected

The study will be conducted at approximately 3-4 CHOP primary care practices in Philadelphia. Recruitment will stop when approximately 55 subjects are enrolled.

3.4 Study Population

We plan to recruit 3-4 urban CHOP-affiliated pediatric practices from CHOP's Pediatric Research Consortium (PeRC) to participate in the study. These practices care for a diverse, complex urban population and have onsite social worker to assist with family crises. Using well-established methods that have proven effective in multiple large-scale trials, 3-4 practices located in Philadelphia will be recruited to participate using letters of invitation and in-person presentations. Incentives to participate will include provider education on parent-child shared reading. A total of 55 eligible children and their parents will be recruited from participating practices to achieve a diverse sample of children. Inclusion and exclusion criteria for Phase 1 will be the same as Phase 2. Children will be eligible to participate if they are 6-24 months old, and have a parent with daily access to a smart phone in order to receive and send text messages.

3.4.1 Inclusion Criteria

Parent who:

- 1) Have an infant aged 6-24 months
 - 2) Have access to a smart phone with text messaging capabilities
-

- 3) Have completed an informed consent

Children who:

- 4) Are aged 6-24 months old

3.4.2 Exclusion Criteria

Parents who:

- 1) Non-English speaking

Children who:

- 1) Were born premature (estimated gestational age < 35 weeks)
- 2) Have been diagnosed with congenital malformations or genetic syndromes which place them at risk for developmental delays

Subjects that do not meet all of the enrollment criteria may not be enrolled. Any violations of these criteria must be reported in accordance with IRB Policies and Procedures.

4 STUDY PROCEDURES

4.1 Phase 1 Rapid-Cycle Design

Informed Consent: Parents will participate in-person consent visits. In the event that the baseline visit cannot be completed in-person an alternative method of obtaining informed consent electronically through REDCap will be used. Modified Verbal consent will be collected if the COVID-19 pandemic persists to limit study staff exposure. Parents will be called to obtain verbal consent for participation using the written informed consent document. Parents who agree will be sent the written consent form for signature through RedCap. In the event that the baseline visit is conducted remotely, parents will be given the option to complete the interview over the phone.

Review of Inclusion/Exclusion Criteria

Interview: The interviews will be audio recorded and transcribed. We will be using ADA Transcription services. The outline of content of the interview will use open-ended questions to identify specific behavioral barriers to more frequent reading with children (see appendix 3 for Interview Guide). Data from the interview will be used to edit reminder messages and coaching content in phase 2 to address perceived barriers. The interviews will occur in the primary care practice following the completion of their child's well visit, or over the phone if COVID-19 is still ongoing to limit study staff exposure.

Demographics

4.2 Phase 2 Screening/Enrollment (Baseline) Visit

Informed Consent: in-person

Review of Inclusion/Exclusion Criteria

Demographics

Measure of Cognitive Stimulation Provided in the Home – (StimQ-Read)

Parenting Stress Index- short form (PSI-SF)

4.2.1 Phase 2 Two Month Follow-Up

Measure of Cognitive Stimulation Provided in the Home – (StimQ-Read)

Parenting Stress Index- short form (PSI-SF)

CDI

DECA

Satisfaction Rating

Survey

4.3 Study Treatment Phase

Over the course of each subject's participation, the subject will have a baseline and a 2-month follow-up visit. After being screened at baseline, participants will complete demographics, StimQ-Read and PSI-SF. At the follow-up visit, StimQ-Read, PSI-SF, CDI, DECA, Satisfactory rating and survey questions will be completed. If the baseline and follow up study visits cannot be completed in-person, surveys may be administered online through REDCap.

4.4 Unscheduled Visits

Unscheduled visits are not anticipated.

4.5 Subject Completion/Withdrawal

Subjects may withdraw from the study at any time without prejudice to their care. They may also be discontinued from the study at the discretion of the Investigator for lack of adherence to the study visit schedule or any AEs. The Investigator may also withdraw subjects who violate the study plan, or to protect the subject for reasons of safety or for administrative reasons. Additionally, if a subject is enrolled but does not complete the baseline surveys within 30 days of enrollment, they will be disenrolled from the study. It will be documented whether or not each subject completes the study. If the Investigator becomes aware of any serious, related adverse events after the subject completes or withdraws from the study, they will be recorded in the source documents and on the CRF.

5 STUDY EVALUATIONS AND MEASUREMENTS

5.1 Screening and Monitoring Evaluations and Measurements

5.1.1 Medical Record Review

Date of birth

Gestational age, sex, developmental assessments

5.1.2 Other Evaluations, Measures

At the start of phase 2, following written informed consent, participant families will complete a baseline visit. In the event that the visit cannot be completed in person, study procedures may be conducted virtually online through REDCap. Measures of demographic and biological variables (child age, sex, race/ethnicity, family income, maternal education level, and family structure), parenting stress, and the home reading environment will be collected by research staff blinded to randomization assignment at this visit (See Appendix 2).

The Read subscale of the StimQ is a validated 14-item parent self-report questionnaire designed to measure of the home reading environment, at baseline and follow-up for children ages 5 to 72 months of age.²³ The StimQ contains 4 subscales (availability of learning materials, reading, parental involvement in 1 developmental advance, parental verbal responsiveness) and is available in English and Spanish. Internal consistency (Cronbach $\alpha=0.88-0.93$) and test-retest reliability (ICC=0.93) of the StimQ is excellent, and it correlates well ($r=0.55$) with the IT-HOME Inventory, another measure of the home environment.⁷⁸ Poverty will be assessed by examining family income (<100% of the Federal Poverty Level) and maternal education status (\leq High School). Parenting stress will be measured at baseline and at follow-up 2 months later using the Parenting Stress Index-Short Form (PSI-SF).²⁴

Parenting Stress Index-Short Form (PSI-SF): Baseline and follow-up. The PSI-SF is a validated 36-item scale that measures parenting stress. It has been shown to have excellent internal consistency and to be positively associated with maternal psychological distress. Scores on the PSI-SF correlate well with the full PSI. The total score will be used.

MacArthur Communicative Development Inventory (CDI): 2-month follow-up. CDI is a validated parent-report scale of early language development which captures important information including language comprehension, production and grammar.²⁶

Devereux Early Childhood Assessment (DECA): 2-month follow-up. DECA is a validated 33-item parent report of socio-emotional problems used to identify children at risk for language deficits.²⁵

